## APPENDIX B.

### SleepTIGHT phone screening script

#### INTERVIEWER INSTRUCTIONS

Read **bolded** text verbatim. Answer any questions as needed. Record all contacts in the contact log.

If a  is reached at any point, say: **I'm sorry, but unfortunately you are not eligible to participate in this study.** [Explain why they are not eligible if appropriate and indicate reason for ineligibility].

- Not fluent in English
- No diagnosis
- No device to access content
- Age < 18
- Medical condition
- Vision/hearing impairment
- Psychiatric condition
- Moderate/severe
- Low QDRS
- No study partner
- Research study
- Dementia medication change
- Other \_\_\_\_\_

#### INTRODUCTION

Hi, this is \_\_\_\_\_ from the SleepTIGHT study.

*Describe how you got their name and phone number. E.g., \_\_\_\_\_ is a UCSF patient who expressed interest in our program; you recently contacted us about the SleepTIGHT study. Clarify that the program may also be known as Napping, Sleep, and Risk of Alzheimer's Disease if necessary.*

**Is this a good time for me to gather more information about your eligibility for the SleepTIGHT study? It should take about 20 minutes.**

- Yes
- No

If NO or NOT AVAILABLE:

Schedule call-back

Date \_\_\_\_\_ Time: \_\_\_\_\_

If **YES**:

**\*START HERE IF CONTINUING CALL\***

#### BACKGROUND INFORMATION

**Great! Before we get started, can you please tell me your name? [or confirm name if already known]**

**How did you learn about this study?**

- UCSF email/letter (1)
- Facebook/Social Media (2)
- Physician Referral (3)
- Recruitment Partners (4)
- Other (99) \_\_\_\_\_

## DEMOGRAPHIC INFORMATION

**How old are you?** \_\_\_\_\_ years (enter as current age in whole years;  if under 65)

**Do you identify as male or female?**  Male (0)  Female (1)

Other (8) \_\_\_\_\_ Prefer not to answer (9)

**Do you identify as Hispanic or Latino?**  Hispanic/Latino (1)  Not Hispanic/Latino (0)

Other (7) \_\_\_\_\_ Prefer not to answer (8) Unknown/Not Reported (9) \_\_\_\_\_

**What race or races do you consider yourself?** (check all that apply)

White (1)  Asian (2)  Black or African American (3)  Native Hawaiian or Pacific Islander (4)

American Indian or Alaska Native (5)  Other (8) \_\_\_\_\_  Unknown or Not Reported (9)

**How many years of school did you complete?**

Elementary:  1  2  3  4  5  6  7  8

High school:  9  10  11  12  GED

College:  13  14  15  16

Post-graduate:  17  18  19  ≥20

Not sure

## ELIGIBILITY CRITERIA

**Are you able to speak and understand English?**

Yes (1)  No (0)

If NO 

**\*\* Do you have a diagnosis related to memory loss?**  Alzheimer's disease (1)

Vascular dementia (2)  Dementia unspecified (3)  Mixed dementia (4)

Mild cognitive impairment (5)

Not sure, but could ask doctor (6)  Other (7) \_\_\_\_\_

**Do you have history of brain tumor or significant head trauma (including for instance, loss of consciousness >30 minutes?)**

Yes (1)  No (0)

If YES 

**Has a doctor ever diagnosed you with brain infarction?**

Yes (1)  No (0)

If YES 

**Has a doctor ever diagnosed you with any severe psychiatric disorders in the past 2 years such as depression, bipolar disorder, schizophrenia or any others?**

Yes (1)  No (0)

If YES 

Specify which: \_\_\_\_\_

**Has a doctor ever diagnosed you with any major neurological disease such as Parkinsons' multiple sclerosis, epilepsy, or Huntington's disease?**

Yes (1)  No (0)

If YES 

Specify which: \_\_\_\_\_

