Diagnosis and Main Inclusion Criteria	
Inclusion Criteria
 
 
• 1) Age 65+,
 
• 2) evidence of MCI, defined as: self-reported quick dementia rating system (QDRS) - derived global clinical dementia rating score of .5,
 
• 3) adequate visual and auditory acuity to allow neuropsychological testing;
 
• 4) evidence of subthreshold or clinical insomnia, defined as a score of 8 or more on the insomnia severity index,
 
• 5) ability to speak understand and write in English, 6) study partner willing to participate,
 
• 7) capacity to give written informed consent; and
 
• 8) owns one or more smartphone or tablet devices that can be used to access the internet and to participate in video conferences.
 
 
Exclusion Criteria
 
 
• 1) Self-reported diagnosis by a physician of any major neurologic disease such as Alzheimer's disease, other dementia, Parkinson's disease, multiple sclerosis, epilepsy, Huntington's disease;
 
• 2) History of brain tumor or significant head trauma (loss of consciousness >30 minutes);
 
• 3) Evidence (CT or MRI scans within 12 months prior to screening) of brain infarction or other focal lesions; 4) Any comorbid psychiatric conditions or severe personality disorder within the past 2 years (by DSM-V), such as major depression, bipolar disorder, schizophrenia, and other psychotic features;
 
• 5) Any uncontrolled medical conditions or systemic illness that might lead to difficulty complying with the study protocol;
 
• 6) Any concomitant treatment that might confound the results (participants must be off all psychotropic medications, including hypnotic medications, and non-pharmacological treatments, for at least 30 days prior to screening);
 
• 7) History of alcohol or substance abuse within the past 2 years;
 
• 8) Shift workers; and
 
• 9) Any inadequately treated primary or secondary sleep disorders
 

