**Has a doctor ever diagnosed you with Cognitive Impairment?**

Yes (1)  No (0)

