**Are you currently taking any medications for memory loss or dementia?**

Yes (1)  No (0)

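### Exclusion 1, the phone script and the SAP disagree on whether diagnosed dementia bars entry, and the script lists lack of a diagnosis as a reason for ineligibility although inclusion 2 requires none

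*Protocol*

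**What the plan says.** The protocol synopsis sets the criteria. Exclusion 1 reads "Self-reported diagnosis by a physician of any major neurologic disease such as Alzheimer's disease, other dementia, Parkinson's disease, multiple sclerosis, epilepsy, Huntington's disease". Inclusion 2 asks for "evidence of MCI, defined as: self-reported quick dementia rating system (QDRS) - derived global clinical dementia rating score of .5"; it requires no prior diagnosis.

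Appendix B, the phone screening script, puts these into questions. Its neurological item, which carries a stop on yes, is "Has a doctor ever diagnosed you with any major neurological disease such as Parkinsons' multiple sclerosis, epilepsy, or Huntington's disease". A separate item asks "Do you have a diagnosis related to memory loss" and offers Alzheimer's disease and three other dementia categories (answers 1 to 4), MCI (answer 5), an unsure option and a free-text option. Two further items ask "Has a doctor ever diagnosed you with Cognitive Impairment" and "Are you currently taking any medications for memory loss or dementia".

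The list of ineligibility reasons in the Interviewer Instructions includes an entry for having no diagnosis, one for a low QDRS, one for moderate or severe status, and "Dementia medication change". It has no entry specific to a dementia diagnosis.

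The SAP, under Study Aims and Procedures, describes the population as people with MCI or mild Alzheimer's disease. The protocol's Purpose section speaks of MCI only.

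**The concern.** Exclusion 1 rests on what the participant reports, so the phone interview is the natural place to apply it. The item that should apply it leaves out the two diagnoses most likely to arise in a trial of cognitively impaired older adults. The SAP then describes a population that appears to include one of them. A screener working from the synopsis and one working from the script and SAP could classify the same caller differently.

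The no-diagnosis entry works in the other direction. It could be used to turn away people whom inclusion 2 is written to capture.

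Feasibility is the primary outcome. The protocol's Feasibility list opens with the proportion of eligible participants who consent, and SAP section 3 adds eligibility and retention rates. These proportions need one definition of eligible. A mixed definition also changes whom the results describe and adds heterogeneity to the cognitive scores.

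**Working it through.** No sample size, power or error rate is involved, so the check is a comparison of texts.

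1. **Exclusion 1 against the stop item.** Exclusion 1 names six conditions or groups: Alzheimer's disease, other dementia, Parkinson's, multiple sclerosis, epilepsy and Huntington's. The script item names the last four in the same order. The two missing entries are exactly the dementia ones.
2. **Where dementia is recorded.** The memory-loss item captures it in answers 1 to 4. The reason list offers nothing specific under which to record an exclusion on that ground; only general entries, such as a medical condition or other, could be used.
3. **Exclusion 1 against the SAP.** The synopsis bars diagnosed Alzheimer's disease; the SAP plans to study mild Alzheimer's disease.
4. **Inclusion 2 against the reason list.** Inclusion 2 is met by a score. The reason list makes absence of a diagnosis a ground for ineligibility.

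Two hypothetical callers show the result:

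| Source | A: physician-diagnosed mild Alzheimer's disease | B: QDRS-derived rating of 0.5, no diagnosis |
|---|---|---|
| Exclusion 1 | Barred | Not barred |
| Inclusion 2 | Decided by score | Met |
| Neurological stop item | Not named; caught only through its open wording | Not stopped |
| Reason list | No specific entry | Fits the no-diagnosis entry |
| SAP population | Apparently included | Included |

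Caller A gets opposite answers from the synopsis and the SAP, and no clear answer from the script. Caller B qualifies under inclusion 2 but matches a listed reason for ineligibility.

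This differs from the script's inconsistent QDRS bands, where one line marks totals of 2.0 to 6.0 and 6.5 to 12.5 eligible and the closing line accepts only the second band. Agreeing on one band would not settle caller A, because diagnosis and score are separate questions.

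On scale, the documents give only the planned 40 subjects. Each participant whose eligibility is in dispute is 1/40 = 2.5% of the sample. How many there would be is not stated and cannot be worked out.

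**The case against.** **Passing the call is not enrolment.** The script closes by saying more tests are needed. Appendix A describes a second appointment to confirm eligibility, and SAP section 1 has staff assess medical history to determine it. A dementia diagnosis recorded on the call could be acted on then. This stands, and it limits how many people would be misclassified. It does not say which rule those later checks should apply.

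**The stop item is open-ended.** It asks about any major neurological disease, so a caller with dementia could answer yes, and dementia has just been asked about. This also stands: the script does not make exclusion impossible. But an exclusion that depends on the caller or interviewer supplying the missing entries is not applied reliably.

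**The SAP may mean mild disease by QDRS rating, without a physician's diagnosis.** That would soften the clash with exclusion 1. The SAP does not say so, however, and inclusion 2 accepts only a rating of 0.5.

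**The reason list is a weak source.** It gives an age limit of 18 where the script screens at 65, and it does not say which diagnosis is meant. No item visibly stops a caller for having none. So wrongful rejection is possible but not shown to be routine. Nor does the entry contradict exclusion 1, since MCI is among the diagnosis options; its conflict is with inclusion 2.

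A reader might infer two stronger things:

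- *The script deliberately passes dementia diagnoses, because the memory-loss item prints no stop.* The stop symbols are missing throughout the text as supplied, and some evidently stood without an accompanying instruction, so this absence proves little.
- *Callers on a steady dose of a dementia drug simply continue.* The next item, on planned changes over six months, prints its conditional instruction against the answer no. Read literally, a stable caller with no planned change is stopped. That may be a slip, but it cannot be cited as evidence of a path through. The drug question also covers memory loss, so a yes does not imply a dementia diagnosis.

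**Conclusion.** The concern holds in two parts. First, the documents disagree on whether a person with diagnosed mild Alzheimer's disease is eligible: exclusion 1 says no, the SAP population suggests yes, and the script's stop item and reason list do not carry exclusion 1 through. Second, the no-diagnosis reason conflicts with inclusion 2.

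Neither part depends on the lost stop symbols. The first assumes that the SAP's mild Alzheimer's disease includes people with a physician's diagnosis, which is the plain reading. The second assumes that the diagnosis meant is a cognitive one.

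The effect falls on the make-up of the sample and on the eligibility and consent proportions. A reader might want to attach a number of wrongly enrolled participants. The documents do not support one: they give no expected share of callers with a dementia diagnosis and no yield for the later checks. They also do not settle which population is intended, so it should not be presumed that exclusion 1 governs.

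**What to change.** Decide one rule on diagnosed dementia, then make exclusion 1, Appendix B and the SAP population agree with it.

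- **If exclusion 1 stands:** name Alzheimer's disease and other dementia in the neurological stop item, tie answers 1 to 4 of the memory-loss item to the stop, add a matching entry to the reason list, and correct the population in the SAP's Study Aims, Procedures and section 3.
- **If diagnosed mild Alzheimer's disease is meant to be eligible:** amend exclusion 1 to say so, and report results by the diagnosis that the memory-loss item already records.
- **In either case:** remove the no-diagnosis reason or reword it to match inclusion 2, and reconcile the dementia-drug items, including the instruction after the planned-changes question, with the chosen rule.

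The cost is a few wording edits to the script plus a correction to either the SAP population or exclusion 1. No new procedure, visit or data item is needed.

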**Has a doctor ever diagnosed you with Cognitive Impairment?**

Yes (1)  No (0)

**Has a doctor ever diagnosed you with Insomnia?**

Yes (1)  No (0)

**Have you been diagnosed with any sleep disorders (such as sleep apnea, sleep related movement disorders etc.) (yes or no) if yes (have they been treated?)**

No (0)       Yes (1)      If Yes, please describe: \_\_\_\_\_. If YES 

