## STOP-BANG Sleep Apnea Questionnaire

Name \_\_\_\_\_ Height \_\_\_\_\_ Weight \_\_\_\_\_

Age \_\_\_\_\_ Male / Female \_\_\_\_\_

STOP			
Do you SNORE loudly (louder than talking or loud (enough to be heard through closed doors)?	Yes	No	
Do you often feel TIRED, fatigued, or sleepy during daytime?	Yes	No	
Has anyone OBSERVED you stop breathing during your sleep?	Yes	No	
Do you have or are you being treated for high blood PRESSURE?	Yes	No	
BANG			
BMI more than 35kg/m  ?	Yes	No	
AGE over 50 years old?	Yes	No	
NECK circumference > 16 inches (40cm)?	Yes	No	
GENDER: Male?	Yes	No	
TOTAL SCORE			

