**High risk of OSA: Yes 5 – 8**

**Intermediate risk of OSA: Yes 3 - 4**

**Low risk of OSA: Yes 0 - 2**

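### As printed, the phone script appears to stop callers whose sleep disorder is adequately treated, although exclusion 9 would admit them

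*Protocol*

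**What the plan says.** The criteria are in the protocol's opening synopsis table.

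- Inclusion 4 requires "evidence of subthreshold or clinical insomnia, defined as a score of 8 or more on the insomnia severity index".
- Exclusion 9 removes people with "Any inadequately treated primary or secondary sleep disorders". It makes no exception for insomnia.
- Exclusion 6 covers "Any concomitant treatment that might confound the results". Its parenthesis adds that "participants must be off all psychotropic medications, including hypnotic medications, and non-pharmacological treatments", for at least 30 days before screening. It does not say which non-drug treatments are meant.

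The phone script (Protocol, Appendix B, Eligibility Criteria) has a separate yes/no item on diagnosed insomnia, with no branch. The next item asks "Have you been diagnosed with any sleep disorders (such as sleep apnea, sleep related movement disorders etc.) (yes or no" and, for a yes, whether the disorder has been treated. It prints one No/Yes pair, a line for a description and a final *If YES*. The treatment sub-question has no answer box or branch of its own. The script's instructions define a mark that means the caller is told they are ineligible.

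The SAP does not restate or resolve these rules. Under Follow-up and outcome measures it makes eligibility and consent rates part of the feasibility assessment. The protocol lists the share of eligible people who consent among its primary feasibility outcomes.

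**The concern.** The script is the working tool that applies the criteria on the telephone. Exclusion 9 turns on whether a disorder is adequately treated, but no branch of the script item uses the answer about treatment. Two screeners, or one screener and the written criteria, can therefore classify the same caller differently.

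Two things are at stake. One is the population: a group that the protocol admits is turned away and, on one reading, a group that it excludes passes the call. The other is the feasibility result, since eligibility and consent rates depend on who is counted as eligible. Misclassification at the first contact enters those figures directly.

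**Working it through.** The plan states no figure on this point, so the check is a comparison of rules.

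**Is the final *If YES* a stop?** The symbol is missing from the extracted text, so the script's own pattern has to decide.

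- A bare *If YES* or *If NO* follows plainly disqualifying answers: not speaking English, brain tumor or head trauma, brain infarction, severe psychiatric disorder, major neurological disease, recent psychotropic or hypnotic drugs, substance abuse, shift work.
- The items on vision or hearing and on other research studies only ask for a description. They have no second, bare *If YES*.
- The sleep-disorder item has both the description prompt and the bare *If YES*. The second is therefore most naturally a stop.
- The script's list of ineligibility reasons has no sleep-disorder entry. It has none for substance abuse or shift work either, so this does not count against the stop reading.

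**Callers run through both rules, under each meaning of YES**

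| Other sleep disorder | Exclusion 9 | Script, YES = diagnosed | Script, YES = treated |
|---|---|---|---|
| None | admitted | continues | continues |
| Diagnosed, adequately treated | admitted | stopped | stopped |
| Diagnosed, treated inadequately | excluded | stopped | stopped |
| Diagnosed, untreated | excluded | stopped | continues |

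The second row conflicts on both readings. The fourth conflicts on the second reading only.

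**Effect on the eligibility count.** Let N callers reach the item and qualify otherwise. Of these, T are adequately treated, I inadequately treated and U untreated.

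- Written criteria: N − I − U eligible.
- Script, YES = diagnosed: N − T − I − U, an error of −T.
- Script, YES = treated: N − T − I, an error of U − T at the call stage.

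On the second reading the count could be right (U = T) while the people are wrong. The consent proportion stays the same only if those wrongly classified would consent at the same rate as the rest. The documents give none of T, I or U. The only scale available is the planned 40 participants, of whom each is 1/40 = 2.5%.

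**Insomnia.** Someone with clinical insomnia (ISI 15 or more) and no treatment meets inclusion 4 but, read literally, fails exclusion 9. The script passes this person if insomnia is reported only under its own item. A caller who counts insomnia as a sleep disorder would also say yes to the next item.

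**Exclusion 6.** Someone whose other sleep disorder is adequately treated by a current non-drug method is admitted by exclusion 9. The parenthesis of exclusion 6 removes the same person if read alone, and perhaps not if the governing phrase about confounding controls it. The script asks about recent drugs only, so it does not settle the matter.

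**The case against.** The best defense is that the treatment sub-question and the description line have little purpose unless staff use them to judge adequacy, so that in practice exclusion 9 is applied. That may be what happens, but nothing printed tells staff to do so. The psychiatric, neurological and psychotropic-drug items also ask for detail beside a stop, so a description line does not imply discretion. The pattern argument is not perfect either: the item on planned changes to dementia medication carries a bare *If NO* after what looks like the acceptable answer. The script may simply contain branching slips. That would explain the sleep-disorder item but would not make it agree with exclusion 9.

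Four stronger readings are tempting, and the documents do not support them.

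- *Exclusion 6 bars all non-drug treatment.* It is limited by the phrase "Any concomitant treatment that might confound the results" and by a 30-day window. What is missing is the type or purpose of treatment.
- *Exclusion 9 bars everyone whom inclusion 4 admits.* The protocol labels ISI 8–14 as subthreshold, and the separate insomnia item has no stop. The intent is clear, and this is a drafting gap.
- *Undiagnosed apnea passes unchecked.* STOP-BANG has no printed eligibility action and no schedule row, but the QDRS, which defines inclusion 2, has no row either. The PSQI, scheduled at screening, asks about snoring and pauses in breathing. Passing the call is provisional: the script announces further tests, and the SAP has clinical interviews by Zoom to determine eligibility.
- *STOP-BANG's high band alone is informative at age 65 and over.* Everyone scores 1 on "AGE over 50 years old", but scores of 1–2 are still low risk and the next band is "Intermediate risk of OSA: Yes 3 - 4", so the lower bands still separate people.

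The later interview can catch untreated people who pass the call. It cannot recover treated people whom the call has already turned away.

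**Conclusion.** The inconsistency between exclusion 9 and the sleep-disorder item is real and holds on both printed meanings of YES. It rests on one inference, that the lost symbol is the stop mark, which the rest of the script supports well. The effect is on who is enrolled and on the eligibility and consent proportions. Its size is unknown, since any percentage would need a prevalence that the documents do not give. A reader might infer that it biases the comparison of arms. The documents do not support that: the misclassification comes before randomization, and the SAP itself calls its effect estimates imprecise. The missing insomnia exception and the unspecified non-drug treatments in exclusion 6 are smaller wording gaps. The point is worth correcting because feasibility is the primary goal and the change costs almost nothing.

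**What to change.** 1. Replace the sleep-disorder item in Appendix B with two. First: any diagnosed sleep disorder other than insomnia? If yes: is it adequately treated? Stop only on yes followed by no. Unclear answers can go to the eligibility interview that the SAP already provides.
2. Add an exception for insomnia to exclusion 9, so that it does not literally conflict with inclusion 4.
3. State in exclusion 6 which non-pharmacological treatments are meant and reconcile it with exclusion 9. Leave the requirement on psychotropic medication as it stands: limiting the whole of exclusion 6 to insomnia treatments would loosen it. Which treatments belong there is for the sponsor to decide.

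If the sponsor did intend every diagnosed sleep disorder to exclude, exclusion 9 has to say so instead. The two texts must agree either way.

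The cost is one script item and the wording of two criteria, with no new instrument or visit. The protocol does not define adequate treatment, so screeners will need a short instruction on it. If calls have already been made, the description lines may allow stopped callers to be recounted.
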